3.2.2. Study population

Inclusion criteria

The inclusion criteria are the following:

- Patient ≥ 18 years.
- Patient for whom a CT-guided intervention in lung has been prescribed and consensually agreed by a multidisciplinary team of radiologists, surgeons and clinicians.
- Patient with a signed informed consent.
- Patient covered by a social security system.

Exclusion criteria

The exclusion criteria are the following:

- Patient unable to undergo general anesthesia.
- Pregnant or nursing female.
- Patient already participating in another clinical study.

[figure not shown]
3.2.3. Study duration and flow chart

Study duration per patient

The study will last from patient's informed consent form signature to Visit 5.

Duration can be 10 months to 15 months, depending on the day of patient's informed consent retrieval and the day of Visit 5.

Flow chart of the study

3.3. Investigational device

The investigational sites have an Epione® device in their interventional radiology department. Quantum Surgical will provide the required training and support to the hospital staff, to enable an adequate use of the device for the clinical investigation considering the new destination of use. Furthermore, operators must have performed CT-guided interventions with Epione® on at least five patients to envisage their participation to the investigation. During the study, if any defect in the investigational device is observed, the study manager must be informed.

The Epione® device is an image-guided robotized device that assists the physician during CT-guided interventions. It provides guidance of rigid straight instruments compatible with the diameter of the needle guide supplied by Quantum Surgical. It allows the physician to plan the insertion of needles or probes from medical images and provides stable, accurate and reproducible guidance in accordance with the planning.

See Clinical Investigation Plan Section 6 for complete investigational device description.

3.4. Sample size justification

The sample size rationale is the following:

The previous pilot study on the Epione® was performed on 20 PP patients (22 ITT) with one or two liver lesions [1].

In addition, a clinical study was conducted on the MAXIO by Smakic *et al.* in 2018 [2], which evaluated all types of interventions with the device, and was performed on a consecutive series of 55 patients using the Robot CT-Guided arm (and then compared to retrospective data from manual interventions).

A PMCF study (QS-NIS-G-H-2101) on the Epione® device is in progress in 2022, it aims to collect clinical data on the performance and safety of the procedures performed with the Epione® device in the abdomen with a target of 55 patients with various indications.

The present study aims to collect clinical data on the performance and safety of procedures performed with the Epione® device used outside of its current indication, for an extension of the indication to the thorax (lungs). Thus, it was decided to define the sample size by an inclusion window of 8 months, with a target of 25 patients (at least one CT-guided intervention in the lungs per patient) considering the inclusion rate of the center.

3.5. Criteria for evaluation planned in the clinical investigation plan

3.5.1. Primary Variable

The primary objective of the study is the the **feasibility of the Epione® device** in assisting needles insertion in CT-guided intervention in the lungs.

The primary endpoint to feasibility is the technical success of the intervention per lesion assessed from **the percentage of robotically assisted lesion targeting and needle placements that were accurate enough to allow the percutaneous intervention.**

The technical success of the intervention will be described by lesion with a Boolean, YES or NO answer to the question:

"Is/are the needles positioned accurately enough to allow next step of the intervention?

3.5.2. Secondary Performance Variables

- Needle placement accuracy per needle after adjustment(s):**

Estimation of distance from target on the planning (planned needle tip position) to real needle tip on the control CT-scan (scan 3) performed after complete robotic needle(s) insertion and adjustment(s).

Estimation of distance from planned needle tip position to target tumor center compared to needle tip position to target tumor center on the final CT-scan performed after complete robotic needle(s) insertion and adjustment(s).

Estimated deviation distance: method

The operator will perform an estimation of the deviation between planned needle and the corresponding inserted needle on the control CT-scan (scan 3) performed after complete robotic needle(s) insertion and adjustment(s), to be representative of the

practice (the interventional radiologist only carries out the intervention when he/she considers the needle position being acceptable in regard with his/her objectives).

On the final CT-scan, the operator identifies the point he/she targeted on the planning, the presumed position is located by memory with the help of anatomical structures surrounding the area. Following collected distances are:

- 3D deviation (3D distance from inserted needle point to planned needle point): estimation and measure.
- Lateral deviation (distance from orthogonal projection of planned needle point to needle axis): estimation and measure.
- Depth deviation (distance from orthogonal projection of planned needle point to inserted needle point on needle axis): estimation and measure.

In addition, the 3D distance from needle tip to lesion center (estimation) is also collected.

- **The number of needle adjustments and grading to reach the target**

The adjustment can be:

- MINOR: Adjustment in depth, in the axis of the needle(s) (advance or retrieve).
- MEDIUM: Lateral adjustment, the needle does not leave the patient's body.
- MAJOR: Total removal of the needle(s) from the patient's body and reinsertion of the needle following the same planned trajectory, or a new trajectory to reach the target.

- **Post-intervention ablation success (ablation only)**

The per-intervention ablation assessment is performed between the pre-interventional and final post-interventional CT-scan (scan 4), in order to determine if the ablation is complete, incomplete or unclear, defined as the following:

- COMPLETE ABLATION: Ground glass opacity (GGO) induced by the ablation completely covers the targeted tumor minimal 5 mm ablation margins.
- INCOMPLETE ABLATION: GGO covers the targeted tumor but with a margin of <5 mm.
- UNCLEAR ABLATION: Margins cannot be assessed, or the delimitation is not identifiable.

- **Long-term local performance of ablation at 6 and 12 months (ablation only)**

Long-term local performance of ablation is based on local tumor progression (LTP) evaluated from CT images at the 6 and 12 months' Follow-up visit. Follow-up visit at 1 month will be taken as baseline.

3.5.3. Secondary Safety Variables

All AEs related to the device or the intervention will be collected.

AEs are categorized in six classes defined below:

Minor complications

- **A:** No therapy or nominal (non-substantial) therapy.
- **B:** Moderate escalation of care, requiring substantial treatment, under conscious sedation, blood product administration, extremely prolonged outpatient observation or overnight admission after outpatient intervention not typical for the intervention.

Major complications

- **C:** Marked escalation of care, *i.e.* hospital admission or prolongation of existing hospital admission for > 24 hours, hospital admission that is atypical for the intervention, inpatient transfer from regular floor/telemetry to intensive care unit or complex intervention performed requiring general anesthesia in previously non-intubated patient (< 48 h).
- **D:** Marked escalation of care, *i.e.* hospital admission or prolongation of existing hospital admission for > 24 hours, hospital admission that is atypical for the intervention, inpatient transfer from regular floor/telemetry to intensive care uni, or complex intervention performed requiring general anesthesia in previously non-intubated patient (> 48 h).
- **E:** Life-threatening or disabling event.
- **F:** Patient death or unexpected pregnancy abortion.

3.5.4. Other Variables

- Demographic data (age, gender).
- Physical examination (weight, height, body mass index).
- Pregnancy test result (if applicable, confirmed by the operator, no test required for the investigation)
- Medical/surgical history (related to disease for the previous 3 months).
- Concomitant treatment/therapy (potentially impacting the intervention for the previous 3 months).
- Comorbidities (potentially impacting the intervention for the previous 3 months).
- Type of intervention planned to require percutaneous needle placement in the thorax (ablation, biopsy, fiducial markers insertion, abscess drainage).

- Targeted tumor for lung intervention: primary cancer (type, stage) or metastatic (origin) or unidentified.
- Information of targeted lesions: number, size(s), location(s), side, lobe, estimated intra parenchymal distance, intervention performed).
- Tumor ablation (type of thermal ablation, material used, duration, post-ablation CT scan).
- CT-guided needle placement (date, operator name, needle identification and size, images pre-and intra-intervention, intervention timing from beginning of the robotically-assisted intervention (switch subject device on) to per-intervention image assessment, intervention timing from beginning of the planning to per-intervention image assessment, device malfunction(s).

3.6. Coding

All AEs will be coded using MedDRA version 25.1 (September 2022).

All concomitant treatments will be coded using WHODrug version March 2022.

4. CHANGES IN THE CONDUCT OF THE STUDY OR PLANNED ANALYSES

4.1. Changes in the conduct of the study

Any amendment to the clinical investigation plan will be described in the study report.

4.2. Changes in the planned analyses

Any major/minor changes from the SAP will be discussed in the study report.

Definitions of the Per Protocol population and the Safety Population have been slightly modified from the definition in the protocol, indeed it has been clarified by the Sponsor that treated patients include all patients with an assistance of at least one needle placement with EPIONE®, even if the procedure (ablation, biopsy, fiducial placement or abscess drainage) was not performed using the EPIONE® device in accordance with protocol specifications.

5. GENERAL ANALYSIS METHODOLOGY

5.1. Study periods

First patient included: 30 November 2022.

Planned recruitment time: 6 months.

Planned last patient completed: Q1 2024.

5.2. Definition of protocol deviations

The protocol deviations will be listed by the statisticians when data collection ends. The deviations will then be categorized as major or minor during the interim/final Data Review Meeting (DRM) prior to locking database.

5.3. Analysis populations

Four different analysis populations are foreseen:

Screened Population

All patients who are proposed to enter the study.

Intention-to-Treat (ITT) Population

All screened patients who have confirmed their signed informed consent and are planned to be treated using the Epione® device.

Per Protocol (PP) Population

All patients in the ITT population treated by the Epione® device, including those for which the procedure was not completed with the Epione® device, without any major deviation.

Safety Population

All patients in the ITT population treated by the Epione® device, including those for which the procedure was not completed with the Epione® device.

5.4. Database lock

Interim and final database locks will be executed after resolution of all queries related to data and after the DRM is held. Database locks will be performed electronically using ENNOV Clinical V8.0 by Delta Consultants' data management team following Delta Consultants' SOPs.

5.5. Statistical concerns

The statistical analysis will be performed by an external CRO (Contract Research Organization: Delta Consultants, Eybens, France). All statistical analyses will be produced using SAS® 9.4 software (Cary, NC, USA).

Results will be presented using tables and listings in two Word documents.

5.5.1. Summary statistics

Description of relevant study variables will be performed using n, number of missing data, mean, standard deviation, median, min and max for quantitative variables and

using number of missing data, frequency and percentage of non-missing for qualitative variables.

Analyses will be presented by patient, by lesion (when relevant) and/or by needle (trajectory). The statistical analysis will take into account data clustering (e.g. several procedures for a given patient) in case of inferential statistics.

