3.2. Study design

3.2.1. Study design and device

This is an interventional, prospective, non-comparative, non-randomized and single-arm study of a CE marked device, used outside of its intended use according to the Medical Devices Regulation MDR (EU) 2017/745.

The Epione® device is a Class IIa, non-invasive device and, as such, falls into Case #1 of the ANSM categorization (pre-market study category 1).

Eligible patients scheduled for an Epione® CT-guided intervention in the lung from the investigator's site will be proposed to participate. If they agree, they are enrolled. In case

the prescribed intervention is not maintained, the patient will be removed from the study without any impact on the inclusion window.

The inclusion period (recruitment) is estimated as 6 months for 25 patients (*i.e.* at least 25 CT-guided interventions in the lungs: at least 1 per patient). The inclusion rate will depend on the number of sites using the Epione® device routinely. Two study sites in France are expected to participate in this clinical investigation, Gustave Roussy (Villejuif) will be the coordinating center and a second site will be the Hôpital de La Timone (Marseille).

Considering the main criteria is feasibility, a technical failure of the whole intervention (for all the lesions planned in case of multiple lesions) leads to patient's premature end of study and study withdrawal. In this case, the only data available and analysable will be the technical success of lesion treatment (primary endpoint).

The study device is a user-controlled, stereotactic accessory intended to assist in the planning and manual advancement of the needle, as well as aiding the verification of needle position during CT-guided percutaneous ablation procedures.

The operating principle of the investigational device is detailed in section 6.2 of the protocol.

Five visits will be recorded in the CRF.

- **Visit 1** (within one month before treatment): the first visit is planned to screen the patient, present the study, and deliver the information notice and informed consent form.

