5.5.4. Handling of dropouts and missing data

Missing data will not be imputed, except dates (missing day) if needed in order to calculate durations.

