9.1. Primary endpoint

9.1.1. Definition of the primary variable

The primary endpoint is the technical success by lesion of each intervention.

Technical success by lesion is defined as:

When the needle(s) tip(s) reach(es) the target(s) with sufficient accuracy to pursue the intervention, and:

- Robotic needle insertion is performed without adjustment.
- Robotic insertion with only minor or medium adjustment(s).
- Robotic insertion is performed with one robotic major adjustment.

Technical failure by lesion is defined as:

When the needle tip does not reach the target with sufficient accuracy to pursue the intervention:

- If insertion of one or several needle(s) from the skin is fully manual.
- Failure of a robotic major adjustment.

The parameter of the primary endpoint consists of the percentage of robotically assisted lesion targeting and needle placements that were accurate enough to allow the percutaneous intervention.

The investigator will describe the technical success of the procedure for each lesion on a 2-point scale:

- "Is/are the needles positioned accurately enough to allow next step of the intervention?" = "Yes"
- "Is/are the needles positioned accurately enough to allow next step of the intervention?" = "No"

The performance endpoint is defined by "Is/are the needles positioned accurately enough to allow next step of the intervention?" = "Yes".

Note: if a lesion cannot be treated because of a major pneumothorax on the previous lesions treated, the lesion is excluded from the study and is not taken into account in feasibility statistics (negative answer to the question "Was the CT-Guided intervention maintained" with "pneumothorax" as reason specification).

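### A lesion with no answer to the primary accuracy question would leave the ITT success rate, because the SAP states neither a lesion denominator nor a rule for blanks

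*SAP*

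**What the plan says.** The primary variable is the investigator's Yes/No answer, per lesion, on whether the needles are placed well enough to go on (SAP 9.1.1). SAP 9.1.2 reports the frequency and percentage of Yes with a 95% CI.

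Two general rules govern the calculation:
- SAP 5.5.1 describes data "using number of missing data, frequency and percentage of non-missing for qualitative variables".
- SAP 5.5.4 states: "Missing data will not be imputed, except dates (missing day) if needed in order to calculate durations".

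SAP 9.1.2 modifies neither rule. SAP 5.3 defines ITT by patient (confirmed consent, Epione use planned) and gives no rule for lesions.

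Technical failure opens with a general condition, "When the needle tip does not reach the target with sufficient accuracy to pursue the intervention", followed by two entries: "If insertion of one or several needle(s) from the skin is fully manual" and "Failure of a robotic major adjustment" (SAP 9.1.1, repeated in 3.2.1). The one lesion exclusion written into the endpoint is the note on a lesion that cannot be treated because of a major pneumothorax from a lesion treated before it.

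**The concern.** The accuracy question assumes that needles are in position to be judged. If the device breaks down, or an attempt is stopped with no needle left in place and no manual insertion, the question has no obvious answer and may stay blank. The SAP expects uncompleted attempts: the PP and Safety definitions (5.3) keep patients whose procedure was not finished with the device, device dysfunction is an end-of-study reason (6.1), and it has its own listing (10.1.2).

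Under 5.5.1 and 5.5.4, a blank leaves both numerator and denominator of Table 3.1.1. In a feasibility study, a blank after a lesion was planned for the device is more likely to be a failure than a success, so dropping it would push the rate upwards. The study has one arm and no performance goal, so this percentage and its interval are the whole primary result. They also appear in both interim reports, which SAP 5.5.5 intends for regulatory use.

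**Working it through.** The SAP has no figure to reproduce here. Section 3.4 sets the 25 patients by inclusion window and rate, with no expected success rate or target precision. What follows is a sensitivity calculation.

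**Inputs**
- Patients: 25, each with at least one intervention (SAP 3.4).
- Lesions, n: not given. Assumed 25 (one per patient), with 35 as an alternative.
- Blank answers, m, and recorded No answers, f: not given. Varied.
- Interval method: not named in 9.1.2. Assumed exact (Clopper-Pearson), two-sided 95%, lesions independent.

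**Formulas**
- SAP rule: (n − m − f) / (n − m).
- Blank counted as No: (n − m − f) / n.
- With f = 0 the SAP rule always returns 100%, and the two rates differ by m/n. With n = 25 each blank costs 1/25 = 4.0 points; with n = 35 it costs 1/35 = 2.9 points.
- When every answered lesion is a Yes, the exact lower limit over k answered lesions is 0.025^(1/k). For k = 24 this is 0.025^(1/24) = 0.858.

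**Results**

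| n | recorded No | blank | SAP rule (95% CI) | blank = No (95% CI) |
|---|---|---|---|---|
| 25 | 0 | 0 | 25/25 = 100% (86.3–100) | 25/25 = 100% (86.3–100) |
| 25 | 0 | 1 | 24/24 = 100% (85.8–100) | 24/25 = 96.0% (79.6–99.9) |
| 25 | 0 | 2 | 23/23 = 100% (85.2–100) | 23/25 = 92.0% (74.0–99.0) |
| 25 | 1 | 1 | 23/24 = 95.8% (78.9–99.9) | 23/25 = 92.0% (74.0–99.0) |
| 35 | 0 | 2 | 33/33 = 100% (89.4–100) | 33/35 = 94.3% (80.8–99.3) |

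With no blanks the two rules agree. With one blank in 25, the lower limit moves by 85.8 − 79.6 = 6.2 points. At the first interim, assuming 10 lesions, one blank gives 9/9 = 100% instead of 9/10 = 90%.

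One lesion per patient leaves no clustering to allow for. With 35 lesions in 25 patients there is some, and SAP 5.5.1 says inference will account for it; the intervals above do not.

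**Which lesions are exposed**
- Tip does not reach the target: meets the opening failure condition, so the answer is No and is counted.
- Converted to fully manual insertion from the skin: a listed failure, counted.
- Not treated because of an earlier pneumothorax: excluded by the written note.
- Planned for Epione, intervention maintained, question unanswered: no rule, so 5.5.1 removes it.

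Only the last group is at issue.

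**The case against.** A reader might infer something stronger: that abandoned robotic attempts have no place in the failure definition, so that lesions the device could not complete drop out in general. The documents do not support this. The opening failure condition in 9.1.1 already covers an attempt whose tip falls short of the target, and manual conversion is listed. SAP 3.2.1 says of a technical failure of the whole intervention: "In this case, the only data available and analysable will be the technical success of lesion treatment (primary endpoint". The plan therefore means failures to stay in the primary endpoint.

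A reader might also take the wording "percentage of robotically assisted lesion targeting and needle placements that were accurate enough to allow the percutaneous intervention" as limiting the denominator to completed robotic placements. The same section counts fully manual insertion as failure, so that reading fails too.

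Other points in the plan's favour:
- A blank would be visible. SAP 5.5.1 reports the number missing, 5.4 requires queries to be resolved and a data review meeting before each lock, and Listings 3.1 and 4.6 cover the primary endpoint and device dysfunction.
- The documents do not show whether the CRF permits a blank.
- There is no threshold or hypothesis for a shifted percentage to cross, and the SAP does not rank ITT above PP.

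All of this stands, and it narrows the point and lowers its weight. It does not close the gap. Query resolution needs a rule for what to enter when no needle is in place, and none is given. A reported missing count still lies outside the headline rate and its interval.

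**Conclusion.** The point holds for unanswered lesions only. Followed as written, SAP 5.5.1 and 5.5.4 let a blank primary answer leave the ITT success rate, which amounts to a second lesion exclusion that 9.1.1 does not state. The bias is upwards if blanks tend to be failures, which is likely but cannot be shown from the documents.

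The size is unknown because the number of blanks is unknown and may be zero. Under the assumption of 25 lesions with no recorded No, one blank is worth 4.0 percentage points and two are worth 8.0. The exact intervals rest on independent lesions. Severity is minor: the plan's intent is clear, missing counts are reported, and no decision threshold depends on the result.

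**What to change.** In SAP 9.1.2, state that:
- the ITT denominator is every lesion planned for Epione in an ITT patient whose intervention was confirmed as maintained on D0, with the existing pneumothorax note as the only lesion exclusion;
- an unanswered primary question counts as No in the ITT analysis;
- the percentage of non-missing answers appears in Table 3.1.1 as a sensitivity row;
- unanswered lesions are shown with reasons in Listing 3.1.

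The denominator should start from lesions planned for the device, in line with the ITT definition in 5.3. Starting from lesions where insertion had begun would lose a breakdown before insertion. No new failure category is needed. If the failure definition is clarified all the same, 3.2.1 and 9.1.1 should change together, since both carry it.

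The cost is a few sentences and one derived flag. The stated success rate may be slightly less favourable, and a blank unrelated to the device would also count against it; the sensitivity row and listed reasons let a reader see that. If no blanks occur, the result does not change.
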